### **9.2 Sample Size and Randomization**

Sample sizes for each group in the pilot study were determined by focusing on the width of 90%, one-sided confidence intervals, as used previously for pilot projects (109). For **Benchmark 1**, the 20% CR interventions will be considered successful if the mean reduction in DLW-assessed weight-maintaining energy intake (EI) provides evidence that the %CR is >10% of the baseline mean (e.g., >200 kcal/day reduction from 2000 kcal/day). This level was chosen because it is approximately the lower end of the range of CR associated with benefits in animal models. Our **primary outcome** will be absolute rather than relative EI change to avoid the loss of efficiency and power from the direct modeling of ratio measures (110, 111). Analyses will be based on constrained, mixed linear models described in Section 9.5. The primary quantity of interest is whether each group's least squares mean EI one-sided 90% lower confidence interval excludes the mean value for an average 10% reduction in caloric intake based on the mean baseline EI.

**Benchmark 1.** Within the remote CR group with ~30 paired observation (i.e., 10% LTFU), and a conservative SD of 250 kcal/day for change in EI, as calculated from CALERIE, we project a 90%, one-sided confidence intervals will have a lower bound excluding 200 kcal/day (a 10% reduction from a baseline mean of 2000 kcal/day) if we observe a 260 kcal/day or greater reduction (a 13% reduction). In a case where the baseline mean intake is 2500 kcal/day, a 310 kcal/day reduction (12.4%) would result in a confidence interval that excludes a 10% reduction in EI (112). With 20 evaluable participants in the in-person CR group, these percentages increase to 13.7% (for a baseline mean of 2000 kcal/day) and 13% (for a baseline mean of 2500 kcal/day). Note that these calculations assume the ICC capturing the dependence of change in EI resulting from group-based interventions is zero. Should the ICC arising from group-based intervention delivery be large enough to inflate the variance of the within-group mean by as much as 10%, a slightly larger observed decrease in EI will be needed to rule out a 10%

reduction. If the target is met for both CR groups, practical and economic considerations will be considered in developing the intervention for the larger trial.

**Benchmark 2.** We will estimate the proportion of individuals consuming calories within the 8-hour window (+/- 30 min) on 80% of days (i.e., each participant will receive a yes/no categorization as to whether they consumed calories within the window on > 80% of days) based on participants' self-report of first and last meal/snack times. If feasible, this calculation will also be performed using data from continuous glucose monitors. If  $\geq 75\%$  of individuals are compliant at this level, we consider it reasonable to consider that TRE within the window chosen could be sustained for a longer-term trial. With  $N=30$  participants in this group, if the observed sample proportion is 87% or above, the lower bound on the Clopper-Pearson exact 90%, one-sided confidence interval will exclude retention values of 75% or below (112). Here again, in the presence of a positive ICC for TRE 8-hour adherence, there will be an inflation in variance of the mean which will translate into needing observed sample proportions > 87% to exclude a value of 75% or below.

For **Benchmark 3**, we target  $\geq 85\%$  retention in each intervention group based on completion of the 9-month follow-up exam. If the observed sample proportion is 90% or higher ( $N=81/90$ ), Clopper-Pearson exact 90%, one-sided confidence interval will exclude retention values of 85% or below. In the presence of a large, positive ICC for dropout, there will be an inflation in variance of the mean which will translate into needing an observed proportion > 90% to exclude values of ~85% or below.

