### 5.1.3 Use of mHealth App and Tracking Appetite Metrics

Relying on our conceptual model, the interventions will combine specific nutritional and behavioral guidance for each participant to achieve adherence to treatment goals. Coaches and the RD have the ability to select specific nutritional and behavioral/environmental strategies

from a “toolbox” based on individual needs (see the separate toolbox document in MOP). Using the HALLO-P mHealth app, participants in both CR groups will: (a) *track the content of all food* intake and body weight each day for the first two months and then at least every other week thereafter; (b) *receive feedback in near real time* that tracks participants’ daily weights, providing feedback and, when necessary, near real time adaptation to the intervention so that they remain in their personalized “zones of adherence” to the trajectory of weight across time using a predicted model developed by Hall et al. (89); (c) *receive feedback* on total calories, the average daily calories consumed each week, and the average calories consumed each month; (d) *receive reinforcements in real time* for meeting study goals in the form of both “mastery” badges (88) and app notifications; and (e) *following an ecological momentary assessment (EMA) protocol* (i.e., collection of responses in participants daily life with an app) report on several appetite related metrics across the day (this feature is turned-on during the first month of the study and for a week during every month thereafter)—these data will be utilized to provide feedback on patterns of appetite throughout the day.

For the TRE group, participants will use the Feedogram as part of the app to *track the beginning and end of their eating cycle each day along with meals/snacks consumed*, for the first two months and then at least every other week thereafter for month 3-6, and at least one week in each month for months 7-9. The app also enables participants to: (a) receive prompts when outside the zone of adherence for TRE, (b) *receive feedback each day* on their success in meeting the TRE interval; receive weekly and monthly feedback on the %frequency of meeting the TRE interval; (c) *receive reinforcements* for meeting study goals in the form of both badges and app notifications; and (d) *following an EMA protocol* report on several appetite related metrics across the day.

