## 5.4 Adherence Assessment

The primary measure of adherence to the CR regimen will be the change in energy intake from baseline to 9 months calculated using the DLW-measured change in TEE in conjunction with the DXA-measured fat and lean body mass changes over 9 months.

Change in self-reported energy intake will be a secondary adherence measure.

Change in scale-measured body weight in line with our model of expected body mass loss under the assumption of 20% CR is a secondary measure of adherence.

Adherence to the TRE regimen will be assessed through data collected by the Companion App where participants will log occasions of caloric ingestion during waking hours. Participants will be considered compliant if they consumed calories within an 8-hour window on 80% of days. An objective secondary measure of adherence will be through the use of continuous glucose monitoring for 10-day intervals using spiking glucose blood levels as a biomarker of caloric intake.

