Biological sample storage including blood and urine				x			x		x	
D3 creatine dilution (d3cr)				x					x	
Physical performance/strength: Expanded Short Physical Performance Battery (eSPPB) / expanded SPPB, 400 meter walk (fast), grip strength					x					x
24-hour dietary recalls (ASA24)				x					x	
*- TRE only – at ~3mo (weeks 8-12) and ~8 months (weeks 28-32) ^- CR only # Commons signs and symptoms will also be assessed monthly during intervention at the individual sessions.										

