#### **6.2.7 Assessments conducted during intervention:**

- *Continuous Glucose Monitoring.* Continuous glucose monitoring (CGM) will assess time in the fasting state in the TRE group using a continuous glucose monitor (G6 Pro, Dexcom) at approximately 3 months (weeks 8-12) and 8 months (weeks 28-32). The CGM records interstitial glucose concentrations every 5 minutes for up to 10 days and will be in blinded mode so the participant cannot see their values. Although it measures glucose levels in the interstitial fluid – and not blood glucose levels – it has been demonstrated to be accurate in the comparison with capillary blood glucose results with the correlation between CGM and capillary blood glucose results of 0.95 (104, 105). The CGM is placed on the lower abdomen using a one-touch applicator by an unblinded study staff member.
- *Ecological Momentary Assessments of Hunger, Desire to eat and Anxiety* (6 assessments during 7 days of months 1, 4 and 7): Within the mHealth *Companion App* we will prompt participants to complete six brief (<60 seconds) ecological momentary assessments (EMAs) each day (waking, late morning, lunch, afternoon, dinner, bedtime) of hunger, desire to eat, and anxiety during 7 days of months 1, 4 and 7. Participants note their hunger in response to the question “to

what extent are you hungry right now?", with responses ranging from "no hunger" to "extreme hunger". Participants note their desire to eat in response to the question "to what extent do you have a desire to eat right now?" with responses ranging from "no desire" to "extreme desire". Anxiety will be rated in response to the question "how anxious do you feel right now?" with responses ranging from "no anxiety" to "extreme anxiety". All responses are provided using a slider with values (which are hidden to the participant) ranging from 0-1000 to simulate a continuous slider.

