## **9 STATISTICAL CONSIDERATIONS**

### **9.1 General Design Issues**

As suggested by multiple authors (106-108), the design and sample sizes for our HALLO pilot study have been chosen to focus on the feasibility of the design of the targeted full-scale study, rather than on power for hypothesis testing between groups.

During the HALLO pilot, we target the enrollment of approximately 100 participants meeting the inclusion/exclusion criteria to one of three intervention arms 1) 20% CR delivered in-person; 2) 20% CR delivered remotely via video conferencing; and 3) 8-hour TRE with *ad libitum* calorie intake for the first 3 waves (66pts) and the fourth wave will randomize ~24 pp to one of two intervention arms including 20% CR delivered remotely and 8-hour TRE groups. We anticipate randomizing 22:34:34 participants with fewer participants being in the in-person CR group since our group (and others) has more experience with that intervention. From those randomized, we anticipate approximately 20:30:30 participants to complete both pre-and post-measures at 9 months. Data from the enrollment process will be used to refine recruitment criteria, estimate recruitment yields, and test and refine intervention approaches. The pilot will inform three design benchmarks: **a)** The degree of sustained CR (**Benchmark 1**): CR > 10% at 9 months; **b)** TRE sustainability (**Benchmark 2**): At least 75% of participants eating within window on >80% of days; and **c)** **Benchmark 3**: Retention > 85% at 9 months.

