For **Benchmark 2**, we will use Clopper-Pearson 90% (80%), one-sided confidence intervals to provide a lower limit on the estimate of the proportion of individuals consuming calories within the 8-hour (+/- 30 min) window on 80% of days (i.e., each participant will receive a yes/no categorization as to whether they consumed calories within the window on > 80% of days) based on self-report. Marginal models for binary outcomes will also be used to explore the magnitude of the ICC for this outcome. This calculation will also be performed using proportion of days as a continuous outcome based on self-report or data from continuous glucose monitors (TRE group). When considered a continuous outcome, methods identical to those outlined for Benchmark 1 can be used.

For **Benchmark 3**, the primary outcome will be the proportion of participants that complete the 9-month follow-up exam. As for Benchmark 2, Clopper-Pearson exact 90%, one-sided confidence intervals will be used to put lower limits on these estimates. Marginal models for binary outcomes will also be used to explore the magnitude of the ICC for this outcome.

Supporting analyses will also be carried out within subgroups defined by sex and race/ethnicity.

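### Applying the Benchmark 2 yes/no adherence rule (>80% of days) to continuous glucose monitoring is unreliable with only 10 to 20 monitored days per participant

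*Combined protocol and SAP*

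**What the plan says.** Section 9.1 sets Benchmark 2 as "At least 75% of participants eating within window on >80% of days". Section 9.2 makes this a rule per person, based on self-reported first and last meal or snack times: "each participant will receive a yes/no categorization as to whether they consumed calories within the window on > 80% of days". The following sentence extends it to CGM: "If feasible, this calculation will also be performed using data from continuous glucose monitors". Section 9.2 then states that, with 30 participants, an observed 87% lets the exact one-sided 90% lower bound exclude 75%.

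On the device, section 6.2.7 says: "The CGM records interstitial glucose concentrations every 5 minutes for up to 10 days". Sections 6.1 and 6.2.7 schedule two wears, in the TRE arm only, at weeks 8-12 and weeks 28-32. No section says whether the wears are pooled, how many valid days are needed, or how a partial day counts.

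The cut-off is worded in two ways. Sections 9.2 and 9.5.1 each contain both 80% and >80%, and section 5.4 has: "Participants will be considered compliant if they consumed calories within an 8-hour window on 80% of days".

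Section 9.5.1 ties the yes/no calculation to self-report and uses CGM differently: "This calculation will also be performed using proportion of days as a continuous outcome based on self-report or data from continuous glucose monitors".

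On app logging, section 5.1.3 asks TRE participants to track eating times for the first two months, then at least every other week in months 3-6, then "at least one week in each month for months 7-9". The Précis, section 5.1.2 and the last paragraph of 5.1.3 instead have TRE participants log each day.

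**The concern.** A cut at 80% of days works well when each person contributes many days. On 10 days, more than 80% means at least 9, because 8 of 10 is exactly 80%. One extra missed day then changes a participant's class, so people well above the cut are often classed non-compliant and people below it are sometimes classed compliant.

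Sections 5.1.2 and 5.4 name CGM as the objective adherence marker for TRE. If its yes/no figure is set beside the self-report figure, or beside 75%, the two can disagree only because one rests on 10 to 20 days and the other on many more. A reader could not separate that from over-reporting in the app. If the second wear shares few days with the log, a same-day comparison would not settle it either.

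**Working it through.** **The plan's own figure.** The one-sided 90% Clopper-Pearson lower bound for x of n is the 10th percentile of Beta(x, n − x + 1). For 26/30 (86.7%) it is 0.751, which excludes 75%; for 25/30 it is 0.713, which does not. The stated 87% is reproduced.

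**Inputs from the documents.** Up to 10 days per wear and two wears (6.2.7); cut-off >80% of days (9.2); 30 TRE completers (9.1); 26 of 30 needed (9.2).

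**Assumptions, not in the documents.** True adherence of 75%, 85% or 90% of days; independent days; CGM reads every day correctly. For the self-report comparator, minimum logging is counted as about 60 days in months 1-2, half of about 120 days in months 3-6, and 3 × 7 = 21 days in months 7-9: 60 + 60 + 21 = 141 days.

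**Probability of being classed compliant.** This is P(X ≥ r) for X ~ Binomial(n, p), with r the smallest count strictly above 0.8n. For n = 10, r = 9; for n = 20, r = 17; for n = 141, 0.8n = 112.8 and r = 113. For example, at p = 0.90 and n = 10: 10 × 0.9^9 × 0.1 + 0.9^10 = 0.387 + 0.349 = 0.736.

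| True share of in-window days | One wear (≥9/10) | Both pooled (≥17/20) | Minimum log (≥113/141) |
|---|---|---|---|
| 75% | 0.24 | 0.23 | 0.09 |
| 85% | 0.54 | 0.65 | 0.95 |
| 90% | 0.74 | 0.87 | >0.99 |

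Counting the minimum log as 137 to 141 days moves the last column only to 0.93-0.95 at 85% and 0.07-0.09 at 75%.

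**Group level.** If all 30 truly adhere on 90% of days, the chance that at least 26 are classed compliant is P(X ≥ 26) for Binomial(30, 0.736) = 7% on one wear, and for Binomial(30, 0.867) = 63% pooled. At 85% it is below 1% either way.

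**Details left open (at 90% true adherence).**
- 10 days read as ≥80% (at least 8): 0.93, against 0.74 for >80%. The looser reading also passes a 75% adherer with probability 0.53.
- 9 usable days (at least 8): 0.775; 8 usable days (at least 7): 0.813.
- Both 10-day wears required to pass: 0.736² = 0.54.

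**Participants who differ.** With a beta-binomial spread around a mean of 90% (intra-person correlation 0.05 to 0.30, assumed), the true share of people above 80% runs from 0.91 down to 0.82. CGM would class 0.73 to 0.78 as compliant on one wear and 0.79 to 0.81 pooled. The shortfall is about 5 to 18 points on one wear and 2 to 10 points pooled.

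**The continuous alternative.** At a mean of 90% over 30 × 20 = 600 person-days, the standard error of the mean proportion is √(0.9 × 0.1/600) = 0.012 with independent days. With the same correlations the variance is multiplied by 1 + 19 × 0.05 = 1.95 to 1 + 19 × 0.30 = 6.7, giving 0.017 to 0.032. No cut-off is involved, so the short wear adds noise without a threshold bias.

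**The case against.** The strongest reply is that little depends on this calculation. Benchmark 2 is decided on self-report, section 5.4 calls CGM a secondary measure, the sentence in 9.2 is conditional, and the analysis section (9.5.1) already uses CGM on a continuous scale. That stands: it limits the consequence to the quality of the objective check. It does not remove the sentence in 9.2, which still repeats the yes/no calculation on CGM.

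A reader might go further and infer that a CGM yes/no figure cannot work at all, because 74% of uniformly 90% adherers falls below 75%. The documents do not support that. The crossing needs a single complete 10-day wear, the strict cut-off, and everyone at exactly 90% with independent days. Two wears are scheduled, and pooling gives 87%; 8 or 9 usable days, or a ≥80% reading, also give more than 75%. What stands is the misclassification in both directions, and a result that depends on choices the plan leaves open.

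A reader might also infer that the second wear will often share no days with the log. If a 7-day log week and a 10-day wear fall independently within 28 days, the mean overlap is 2.9 days and the chance of none is 37%. That assumes only the minimum in 5.1.3 and random placement, whereas other text asks for daily logging. It concerns only the second wear, and no section makes CGM a day-by-day validation of the app. The documents support only that the logging instructions conflict and that nothing ties logging to the wear.

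**Conclusion.** The point holds as one of reliability and specification. Under independent days and error-free CGM, the yes/no rule on 10 to 20 days classes only 54% to 65% of 85% adherers as compliant, against about 95% on the minimum log, and passes 24% or 23% of 75% adherers, against 9%. Even with every participant at 90%, pooled CGM reaches 26 of 30 only 63% of the time. The size of the downward pull depends on how adherence varies between people, which the documents do not give; across the assumed spreads it is 2 to 10 points pooled. The effect is confined to the secondary, conditional CGM check. It does not alter the self-report result for Benchmark 2, and it does not show that a CGM figure would overturn a true pass. It is worth changing because the better analysis is already in 9.5.1.

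**What to change.** 1. In 9.2, replace the CGM yes/no calculation with the continuous proportion of in-window days from 9.5.1, pooled over both wears. State the minimum number of valid days and how a partial day counts.
2. Do not compare a CGM yes/no figure with 75%. If one is kept, report it descriptively beside the self-report classification cut on the same days.
3. Use one cut-off, either >80% or ≥80%, in 5.4, 9.2 and 9.5.1.
4. Reconcile the logging schedule in 5.1.3 with the daily logging in the Précis, 5.1.2 and the last paragraph of 5.1.3. In 5.1.3 and 6.2.7, ask TRE participants to log meal times on every CGM day, so that same-day agreement can be reported.

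This costs wording and scheduling, with no new device or visit. If only the weekly minimum is logged, it adds about 3 logging days per wear (10 − 7). Participants may behave better on days they know are monitored, which should be noted when the result is read. The mean proportion of days also does not estimate the share of people above 80%; that quantity stays with self-report.

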## 9.4 Outcomes

### 9.4.1 Primary feasibility outcomes

a) Degree of sustained CR (**Benchmark 1**): CR > 10% at 9 months;

- b) TRE sustainability (Benchmark 2):** At least 75% of participants eating within window on >80% of days; and
- c) Retention of study participants (Benchmark 3):** Retention > 85% at 9 months.

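### Benchmark 3 targets at least 85% retention in each arm, but its only precision figure (81/90) pools the three arms, and no section states the level of assessment

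*Combined protocol and SAP*

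**What the plan says.** Section 9.2 states the Benchmark 3 target by arm: at least 85% "retention in each intervention group based on completion of the 9-month follow-up exam". The next sentence gives the section's only numerical statement on retention. It begins "If the observed sample proportion is 90% or higher", gives the count as 81 of 90, and says that the "Clopper-Pearson exact 90%, one-sided confidence interval will exclude retention values of 85% or below".

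The 90 is the whole trial. Section 9.1 says "We anticipate randomizing 22:34:34 participants", and 22 + 34 + 34 = 90. The same section adds that "we anticipate approximately 20:30:30 participants to complete both pre-and post-measures at 9 months".

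The other sections do not settle the level. Section 9.4.1 lists "Retention > 85% at 9 months" and names no arm. Section 9.5.1 says "the primary outcome will be the proportion of participants that complete the 9-month follow-up exam" and that exact 90% "one-sided confidence intervals will be used to put lower limits on these estimates", without saying whether there is one estimate or three.

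**The concern.** A per-arm target and a pooled precision statement are different things, and here they stand in adjacent sentences with nothing to connect them. Benchmark 1 is judged in each CR group and Benchmark 2 in TRE alone, so a reader expects retention to be judged by arm as well. The one figure offered does not describe what an arm of 22 or 34 can show.

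Two things are at stake. A pooled figure near 90% is compatible with one arm well below its target. And with the level unstated, the choice between a pooled and a per-arm reading stays open until the data are in, when the two may disagree.

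**Working it through.** **Inputs.** Arm sizes 22, 34 and 34, and expected completers 20, 30 and 30 (9.1). Target 85%, exact one-sided 90% Clopper-Pearson bound, worked count 81/90 (9.2). I take those with both pre- and post-measures as those retained, and treat participants as independent.

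**Formula.** The lower bound L(x, n) is the 0.10 quantile of a Beta(x, n − x + 1) distribution. When x = n it reduces to 0.10^(1/n).

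**The plan's own figure.** L(81, 90) = 84.67%, and the chance of 81 or more when true retention is 85% is 0.115. So 81/90 narrowly misses under the named method. L(82, 90) = 85.96%, so 82/90 is the smallest count that excludes 85%. The difference is one participant and is a separate matter; both counts are used below.

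**What the pooled count allows in one arm.** At 81/90 there are 9 losses, wherever they fall.
- In-person CR loses 6: 16/22 = 72.7%, with 9 − 6 = 3 losses still allowed among the other 68.
- A 34-person arm loses all 9: 25/34 = 73.5%, with no loss among the other 56.
- At 82/90 (8 losses), a 34-person arm cannot fall below 26/34 = 76.5%, again with no loss elsewhere.

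**How often a weak 34-person arm is hidden.** Let one 34-person arm have true retention of 80% and the other 56 participants a common retention p. Both are assumptions; the documents give neither. The probability that Bin(34, 0.80) + Bin(56, p) is at least 82 is:

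| p in the other arms | probability |
|---|---|
| 88% | 6% |
| 90% | 11% |
| 95% | 36% |
| 97% | 52% |

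The plan's own expectation is 20/22 = 90.9% and 30/34 = 88.2%, so the upper rows are closer to it.

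**The same bound within an arm.**

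| count | observed | lower bound |
|---|---|---|
| 22/22 | 100% | 90.1% |
| 21/22 | 95.5% | 83.4% |
| 32/34 | 94.1% | 85.1% |
| 31/34 | 91.2% | 81.4% |
| 20/22 (expected) | 90.9% | 77.6% |
| 30/34 (expected) | 88.2% | 77.9% |

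Excluding 85% therefore takes 22/22 in the in-person arm or 32/34 in either other arm. If true retention is 95%, these are reached with probability 0.32 and 0.76; if it is 90%, 0.10 and 0.33.

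**The observed target within an arm.** 0.85 × 22 = 18.7, so 19/22 (86.4%). 0.85 × 34 = 28.9, so 29/34 (85.3%), where the lower bound is 74.4%. An arm with true retention of 80% meets its target with probability P(Bin(22, 0.80) ≥ 19) = 0.33 or P(Bin(34, 0.80) ≥ 29) = 0.30.

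**The case against.** The strongest reply is that 81/90 is not a decision rule. Section 9.2 says when the CR interventions count as successful on Benchmark 1, but has no such sentence for Benchmark 3. It sets a per-arm target and then illustrates what an interval would exclude, in a section that sizes the pilot on interval width. On that reading an arm at 26/34 simply fails its target. Sections 9.4.1 and 9.5.1 are silent on the level, not contradictory, and limits on several estimates could mean one per arm. The pilot is described as informing the design of a larger trial, and for that an overall retention figure is legitimate.

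Much of this stands. A reader might infer that an arm losing a quarter of its participants would be declared feasible. The documents do not support that: no sentence makes the pooled count a pass rule, and the per-arm target speaks against it. Nor is such masking the usual outcome. In a 34-person arm a loss of a quarter needs 9 losses, which 81/90 allows only if nobody else is lost and 82/90 does not allow at all. The 52% needs the other arms at 97%; at 90% it is 11%.

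What the reply does not answer is that the stated precision does not hold at the level of the target, that no per-arm count or bound is given, and that no section commits to reporting retention by arm. The supporting subgroups named in 9.5.1 are sex and race/ethnicity.

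**Conclusion.** The concern holds as an unreconciled level of assessment for a primary feasibility outcome. The target is per arm, the only precision figure is pooled, and the exclusion of 85% described for the pooled 90 is out of reach for an arm at its expected retention, where the bounds are about 78%. How often the pooled figure would hide a weak arm depends on assumed retention: about 6% to 52% for a 34-person arm at 80%, and toward the low end at the plan's expected retention. Clustering of dropout within intervention groups, which 9.2 acknowledges, would widen all the bounds. This should be corrected, but it is not evidence that the plan would accept a failing intervention.

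**What to change.** In 9.2, 9.4.1 and 9.5.1, state that Benchmark 3 is assessed in each arm against an observed retention of at least 85% (19/22, 29/34 and 29/34 at the planned sizes), and that each arm's exact one-sided 90% lower bound is reported. Keep the pooled estimate as supportive and label it as pooled.

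State separately, so that the two are not confused, that excluding 85% with confidence within an arm would need 22/22 or 32/34, and that the expected completers give lower bounds of only about 78%.

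The cost is wording and three intervals from data already collected. The downside is a less favourable stated precision. Meeting the observed target does not establish true retention above 85%: the bound at 29/34 is 74.4%, and an arm with true retention of 80% would meet the target about 30% to 33% of the time. In some settings that is more lenient than the pooled count (with the other arms at 90%, a 34-person arm at 80% goes with 82/90 or more in 11% of trials), so the plan should say so and show the bounds beside the observed proportions.

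### Benchmark 3: 81/90 retained does not exclude 85% by the plan's own exact 90% one-sided bound (84.7%); the first count that does is 82/90

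*Combined protocol and SAP*

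**What the plan says.** Section 9.1 defines Benchmark 3 as "Retention > 85% at 9 months" and gives the expected allocation: "We anticipate randomizing 22:34:34 participants", a total of 22 + 34 + 34 = 90.

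Section 9.2 states the target as at least 85% "retention in each intervention group based on completion of the 9-month follow-up exam". It then gives one worked figure for all 90 participants together: with observed retention of 90% or higher (81 of 90), the "Clopper-Pearson exact 90%, one-sided confidence interval will exclude retention values of 85% or below". The next sentence says that a large positive ICC for dropout would "translate into needing an observed proportion > 90% to exclude values of ~85% or below".

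Section 9.5.1 names the same interval for the analysis: "As for Benchmark 2, Clopper-Pearson exact 90%, one-sided confidence intervals will be used to put lower limits on these estimates".

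**The concern.** The worked sentence fixes everything needed to check it: the count, the denominator, the interval method, the confidence level, the side and the value to be excluded. An exact lower bound is conservative, and a gap of five percentage points at n = 90 is close to the limit of what a one-sided 90% bound can separate, so the claim needed recomputing.

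Retention is one of three primary feasibility outcomes, and this sentence is the plan's only worked guide to the observed retention that would exclude 85%. If it is wrong, the protocol promises a conclusion at 81/90 that its own prespecified interval would not deliver.

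**Working it through.** **Inputs.** Count and denominator: 81 of 90 (section 9.2; 90 agrees with 22:34:34 in section 9.1). Method: Clopper-Pearson exact, one-sided, 90% (sections 9.2 and 9.5.1). Value to exclude: 85%. ICC: zero, since the plan treats a positive ICC as a further inflation.

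**Formula.** For x retained out of n, the one-sided 90% lower bound is the 0.10 quantile of a Beta(x, n − x + 1) distribution. Equivalently, a value p₀ is excluded only if P(X ≥ x | n, p₀) is below 0.10.

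**Calibration on Benchmark 2.** Section 9.2 says that with N = 30 an observed 87% or above excludes 75%. For 26/30 (86.7%) the 0.10 quantile of Beta(26, 5) is 0.7510, and P(X ≥ 26 | 30, 0.75) = 0.0979. The plan's figure reproduces, so the formula is the one the plan used there.

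**Benchmark 3.**

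| Retained / 90 | Observed | Exact 90% one-sided lower bound | P(X ≥ x given p = 0.85) | Excludes 85%? |
|---|---|---|---|---|
| 80 | 88.9% | 83.40% | 0.1898 | No |
| 81 | 90.0% | 84.67% | 0.1153 | No |
| 82 | 91.1% | 85.96% | 0.0632 | Yes |

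The shortfall at 81/90 is 85.00 − 84.67 = 0.33 percentage points. The highest one-sided confidence at which 81/90 excludes 85% is 1 − 0.1153 = 88.5%.

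**Could another reading give the plan's result?**

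- Rounding does not help: 81/90 is exactly 90%.
- Reading the level as 90% two-sided (95% one-sided) lowers the bound to 83.20%.
- Other interval types at one-sided 90% do exclude 85%: Wilson 85.20%, mid-P 85.25%, Jeffreys 85.32%, Wald 85.95%. The text names the exact Clopper-Pearson interval.
- An exact one-sided 80% bound would be 86.36%. Section 9.5.1 adds a parenthetical 80% after the 90% level for Benchmarks 1 and 2 but not for Benchmark 3, and section 9.2 gives only 90%.

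**Dependence on N.** Take the smallest count at or above 90% of N. For N from 85 to 120 the rule fails only at N = 90 (84.67%), 91 (82/91, 84.84%) and 92 (83/92, 84.997%). It also fails at each N from 80 to 84. It holds, barely, at N = 100 (90/100, 85.01%).

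**How often it would matter.** The stated and corrected thresholds disagree only when exactly 81 of 90 are retained. With independent dropout, that has probability 0.139 if true retention is 90% and 0.131 if it is 88.9%.

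**If the bound were applied by arm.** The target sentence speaks of each group, whereas the illustration pools all 90. Under the same exact rule with zero ICC:

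| Arm size | Near 90% observed | Bound | First count excluding 85% | Bound |
|---|---|---|---|---|
| 22 | 20/22 | 77.58% | 22/22 (21/22 gives 83.44%) | 90.06% |
| 34 | 31/34 | 81.40% | 32/34 | 85.10% |

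**The case against.** The strongest case on the other side is about consequence. The sentence illustrates precision in a pilot that is not powered for hypothesis tests and has no formal stopping rules. The analysis will compute the bound from the observed data, so the illustrated count never enters it. The recruitment target is about 100, and at 90/100 the sentence is true. The plan itself expects about 20:30:30 = 80 participants with both pre and post measures, and 80/90 fails under either threshold. All of this stands and keeps the point minor. It does not make the sentence correct, because 90 is the denominator the plan chose to print.

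Two narrower objections also have some force. The parenthetical 80% in section 9.5.1 is unexplained. It may only denote the two-sided 80% interval, whose lower limit is the same as that of a one-sided 90% interval. In that case the plan offers no looser level for any benchmark, and the conclusion here is the same on either reading. Second, a target for each arm's observed retention can coexist with a pooled illustration of precision, and the plan nowhere says that the bound must exclude 85% within each arm. The by-arm counts above are therefore conditional: they show why the unit should be stated, not that the plan has set an unattainable rule.

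The ICC sentence is not false in itself, and it refers only to approximately 85%. It does carry over the same 90% reference point.

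**Conclusion.** The worked threshold for Benchmark 3 is wrong as written. At the plan's own N of 90, with zero ICC and the exact one-sided 90% interval that sections 9.2 and 9.5.1 both name, 81/90 gives a lower bound of 84.67% and does not exclude 85%. The smallest count that does is 82/90. The error is one participant in the count, 0.33 percentage points in the bound, and 0.115 against a nominal 0.10 in the tail probability. A positive ICC would push the required proportion higher still.

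Severity is minor, and confidence in the arithmetic is high. The practical risk is limited to a result of exactly 81/90, where the reported bound would contradict section 9.2 and could prompt a dispute over whether the benchmark had been met.

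**What to change.** In section 9.2, replace the 90% (81/90) illustration with 91.1% (82/90), or state the count for the number actually randomized, for example 90/100. Change the 90% reference point in the ICC sentence to match. State whether the confidence bound applies to the pooled sample or to each arm. If it is meant by arm, give the by-arm counts instead.

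The cost is a wording change to the protocol and SAP. The illustrated threshold rises by one participant, with no additional participants, visits or analyses.
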